10.5 Concomitant Therapy

As noted in the exclusion criteria, study participants cannot at the time of study enrollment or in the 6 months prior receive Cognitive Behavioral Therapy (CBT) for pain or a similar psychoeducational skill-based training for pain (nor indicate that they have scheduled to begin such treatment). However once enrolled, participants can receive any pharmacologic or nonpharmacologic treatments available to them without restriction. At each study assessment (3-, 6- and 12-month follow-ups), participants' use of CBT for pain or a similar psychoeducational skill-based training for pain (in-person, by phone or via online or App-based programs) will be assessed.

11 STUDY ASSESSMENTS AND PROCEDURES

Section 8 describes the informed consent process in detail. The consent process will occur prior to initiation of the baseline survey but ideally during the same phone encounter or web survey session as the screening.

11.1 Baseline Assessment

Patient baseline assessment. Patients who consent to participate in the study will be asked to complete the baseline assessment either by phone or online immediately following the informed consent process. The baseline assessment will include the measures described in section 3.1. In addition, the baseline assessment will confirm contact information, collect preferences for the administration mode of follow-up assessments, and assess subjects' willingness to potentially participate in the interviews as part of the qualitative evaluation. It is expected that the informed consent and baseline assessment will take approximately 45-60 minutes.

11.2 Follow-Up Assessments

Patient assessment at the time of notification of randomization. At the time that participants are mailed the materials notifying them of their study arm assignment, they will also be mailed a brief paper survey and a pre-posted return envelope. The paper survey will assess the participants' perceived support of the intervention to which they have been assigned and will serve as the baseline assessment of this potential mediator variable. The paper survey will take no more than 5 minutes to complete. (Note: This assessment is offered only by paper due to the fact that it is mailed with the other materials related to randomization notification and logically it is most feasible to administer this way at this particular time point.)

Patient follow-up assessments at 3-, 6- and 12-months. Based on the preference for survey administration mode (online, phone or paper) indicated at the time of the baseline assessment, participants will initially be sent the follow-up survey via their preferred mode. (Note: At any point during the study, a participant can change their preferred survey mode.) The protocol for follow-up with non-responders within the assessment window will employ the other modes of contact in order to maximize the opportunity to reach participants. For example, subjects who prefer email contact for the assessments will also be contacted by phone if they do not complete the assessment using the web link in the emails within a set period of time. Each follow-up assessment will take approximately 30 minutes to complete. The specific protocol for contacts related to follow-up assessments is described in the study's operating procedures.

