10.1.2 Virtual Coach-led CBT-CP

Overview. The coach-led program includes 8 sessions of CBT-CP provided one-on-one via telephone or video encounters. Each session takes 60 minutes and provides interactive training in one or more evidence-based pain-coping skills. Sessions are scheduled at the participant's convenience with approximately one session per week and participants have the option of meeting with the coach by telephone only, using video conferencing or a combination of the two. The live virtual-enabled coaching provided can enhance patient motivation and engagement. This approach is likely to be especially useful for depressed or anxious patients (common chronic pain comorbidities) for whom de-activation and/or avoidance may create barriers to implementing effective pain-coping skills. Coaches providing these virtual visits are required to have at least master's-level behavioral health training and conduct coaching sessions from the study sites at KPWHRI in Seattle and KP CHR in Portland. This telehealth model of centralized behavioral health services is being widely adopted across health care systems nationally, and thus represents a critically important approach for this active arm of the study.

Onboarding. Following randomization, participants assigned to Virtual Coach-led CBT-CP are mailed materials that include a brief biographical description of their health coach and a participant workbook with handouts for the 8 sessions and materials for logging skills practice. The assigned coach calls the participant approximately one week after the materials are mailed. The primary goal of this outreach by the coach is to introduce themselves and to "onboard" the participant to the program. The onboarding call includes verifying receipt of the packet of materials and orienting the participant to the Virtual Coach-led program structure and format. Participants are informed that coaching calls are confidential, asked their preference for telephone or video coaching calls and for permission to record all coaching calls. The coach will use the onboarding call as an opportunity to respond to questions from the participant and to schedule the first coaching call. Coaches follow specified guidelines to complete the onboarding call which include suggested language/scripting.

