Pain catastrophizing	Pain Catastrophizing Scale (PCS)– Short Form 6 ¹⁵ (6-item; continuous)	Patient self-report at baseline and 3 months
Pain self-efficacy	Self-Efficacy for Pain Management subscale of the Chronic Pain Self-Efficacy Scale ¹⁶ (5-item; continuous)	Patient self-report at baseline and 3 months
Perceived support	2 items; developed in UG3 phase	Patient self-report at notification of randomization and 3 months

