16.0. Additional Effectiveness Analyses for Primary Outcome (Moderators and Mediators)

Moderator (Aim 1b) Statistical Hypotheses: We hypothesize that for patients with more complex conditions (concomitant mood or anxiety disorders; multisite pain) or challenging social / environmental factors (rural/medically underserved or unmet social needs) the contact with a live coach will result in better pain-severity outcomes when compared to those receiving painTRAINER.

Moderator (Aim 1b) Analyses: Subgroup analyses will be conducted to determine the impact of the active interventions on specific populations and explore for potential heterogeneity of treatment effects by sex, age, race/ethnicity, rural/medically underserved residency, multiple pain conditions, mental health mood disorders, and negative social determinants of health. Analyses for Aim 1b will follow the same general approach as for Aim 1 but will be focused on assessing heterogeneity of treatment effects (sub-groups). We will assess heterogeneous treatment effects by each potential moderator separately. For each moderator, we will include in the regression models described in the analytic plan for Aim 1, a main effect for the moderator and an interaction between the moderator, intervention, and follow-up time, to estimate time-specific intervention effects within each subgroup defined by the potential moderator. The primary comparison for Aim 1b will be of the interaction terms associated with each intervention arm at the 3-months follow-up time. The longitudinal nature of data collection will allow us to qualitatively assess if the treatment effectiveness pattern is different over time in each of the intervention groups at the two levels of each of the moderators.

Mediator (Aim1c) Statistical Hypotheses: We hypothesize that changes in pain catastrophizing, pain-related self-efficacy, and perceived support from baseline to 3 months will be mediators of treatment outcomes at 6 months for those in both active interventions.

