Mediator (Aim 1c) Analyses: We will use mediation analyses to assess and quantify the effect of theory-based mediators (pain-catastrophizing, pain self-efficacy, perceived support). Mediators represent a causal pathway between the intervention and outcome. Mediation occurs when the intervention influences a variable (the mediator) that in turn subsequently influences the outcome variable. Controlling for a mediator variable causes the strength of relationship between intervention and outcome to be meaningfully reduced. Consistent with recommendations, we will conduct mediation analyses only for interventions that have significant impacts on the outcomes under consideration at 6 months. Primary mediation analyses will assess the effect of the potential mediators on the primary outcome at 6 months, MCID in pain severity, while explanatory secondary analyses will investigate mediator impacts on secondary outcomes at 6 months. We will conduct mediation analyses using the framework recommended by Baron and Kenney²⁴ but using more recent statistical methods developed to better quantify and decompose different aspects of the mediation effect.²⁵ We will run a separate set of mediator analyses for each intervention compared to usual care. We will illustrate our approach for the binary outcome, achieving MCID in pain severity at 6 months.

Our statistical approach for mediation analysis will be to first demonstrate an association between the interventions and the binary outcome, achieving MCID in pain severity at 6 months (step 1; Aim 1).

Step 1 Model:

$$\log(E(Y_i)) = \beta_0 + \beta_1 Int_i + \boldsymbol{\beta}_z \mathbf{Z}_i$$

where Y_i is the binary outcome achieve MCID in pain at 6 months for participant i ($i=1,\dots,n$), Int_i is 1 if the participant i is randomized to given intervention group and 0 otherwise and \mathbf{Z}_i is a vector of baseline adjustment covariates.

We will then demonstrate an association between the interventions and change in each mediator at 3 months (step 2). To do this, we will construct a regression model for each potential mediator under consideration, with the change between the value of the mediator recorded at 3 months and baseline as the dependent variable including a main effect for the intervention. We will do this for each potential mediator and include in the next step only those mediators that are associated with either intervention group with a p-value less than 0.10 (test based on β_{M1} below).

Step 2 Model:

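### The perceived-support baseline is answered after the arm is disclosed, so the change score subtracts any arm effect already present at notification

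*Protocol*

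**What the plan says.** **When it is measured.** Protocol 11.2: "At the time that participants are mailed the materials notifying them of their study arm assignment, they will also be mailed a brief paper survey". The form is to assess participants' "perceived support of the intervention to which they have been assigned and will serve as the baseline assessment of this potential mediator variable". SAP 4.0 gives the two measurement times as "Patient self-report at notification of randomization and 3 months", and Protocol 3.4 agrees. The other two mediators, catastrophizing and self-efficacy, are taken at the baseline survey and at 3 months. Protocol 4.3 and SAP 8.0 place randomization after baseline data collection, and SAP 13.0 defines baseline variables as pre-randomization.

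**How it is used.** The Aim 1c hypothesis in SAP 16.0 is that changes in catastrophizing, self-efficacy and "perceived support from baseline to 3 months will be mediators of treatment outcomes at 6 months". The steps that matter here are:

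- Step 2 regresses each mediator on arm, "with the change between the value of the mediator recorded at 3 months and baseline as the dependent variable". A mediator goes forward if it is associated with either intervention at p < 0.10.
- Step 3a models arm on the retained changes by logistic regression and turns the fitted probabilities into inverse-probability weights. The weighted and unweighted arm effects on the 6-month outcome are then compared.

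All three mediators are handled alike. Neither document has a separate rule for perceived support.

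**The concern.** A change score isolates what happened after assignment only if its starting value was fixed before assignment. Here it was not. By the time the form is answered, participants know their arm and have been sent arm-specific material: a login and workbook for painTRAINER, a coach biography and workbook for the coach-led arm, a printed guide for usual care. A difference between arms in expected support at that point is plausible, and it would itself be an effect of assignment.

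If such a difference exists, subtracting the notification value takes it out of the mediator. The plan could then understate the arm effect on perceived support, give it the wrong sign, or drop it at the p < 0.10 screen. Because Step 3a weights on all retained mediators together, the joint mediated share would be affected too. A reader of the results could not tell these outcomes from a true absence of mediation.

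**Working it through.** The documents state no effect size, SD or power for the mediation analysis, so there is no plan figure to reproduce. The form of the bias is algebra. Its size rests on assumed values.

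**1. Step 2 coefficient.** Let d0 be the arm effect on perceived support when the notification form is answered, and d3 the effect at 3 months. The arm effect on (3-month − notification) is

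d3 − d0.

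It equals d3 only if d0 = 0, is zero if d0 = d3, and reverses if d0 > d3.

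**2. Passing the screen, one intervention against usual care.** Inputs: 621 per arm (the evaluable number in SAP 5.0). Assumed: SD 1 at both times, correlation ρ = 0.5, d3 = 0.2 SD.

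- SD of change = √(2(1 − ρ)) = 1; SE = √(2/621) = 0.0567; critical value 1.645.
- P(pass) ≈ Φ((d3 − d0)/SE − 1.645) + Φ(−(d3 − d0)/SE − 1.645).

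| Share of d3 present at notification | d3 − d0 | P(pass), ρ = 0.5 | Range, ρ 0.3 to 0.7 |
|---|---|---|---|
| 0% | 0.20 | 97% | 91–100% |
| 25% | 0.15 | 84% | 72–96% |
| 50% | 0.10 | 55% | 44–74% |
| 75% | 0.05 | 23% | 19–31% |
| 100% | 0 | 10% | 10% |

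The 3-month level passes at 97% in every row.

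**3. The SAP's either-arm rule.** The table covers one comparison. The SAP retains a mediator if either comparison passes. The two comparisons share usual care, so their test statistics have correlation 0.5. Under the null, 1 − P(|Z1| ≤ 1.645 and |Z2| ≤ 1.645) ≈ 17.5%. With d0 = d3 in both arms, a true mediator is therefore kept about 17.5% of the time, not 10%.

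**4. Sign reversal.** With assumed d0 = 0.3 and d3 = 0.2, a single comparison is retained with the wrong sign 33% to 74% of the time (400 to 621 per arm, ρ 0.3 to 0.7).

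**5. Share recovered in Step 3.** Assumed: d3 = 0.5 SD, ρ = 0.5, outcome risk about 15%, log relative risk 0.4 per SD of 3-month support, and no other path. Within an arm, the slope of the 3-month level on the change is (1 − ρ)/(2(1 − ρ)) = 1/2, so the share recovered is about ½ × (1 − d0/d3).

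| d0 | ½ × (1 − d0/0.5) | Large-sample simulation of the SAP weights |
|---|---|---|
| 0 | 50% | about 50% |
| 0.25 | 25% | 25% |
| 0.5 | 0% | 0% |
| 0.6 | −10% | −10% |

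The first row matters. Half the share is lost with a clean baseline, because the assumed outcome depends on the level and not on the change. Timing accounts only for the fall from 50%.

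A second simulation (d3 = 0.3, true mediated share about 34%) gave the same pattern. The change score explained 18%, 13%, 9%, 4% and 0.5% as the share present at notification rose from 0 to 100% in quarters. The 3-month level gave 34–35% throughout.

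**The case against.** **d0 may be small.** Sessions start at about Day 8 to 14 (Protocol Table 1), and in the coach-led arm "The assigned coach calls the participant approximately one week after the materials are mailed", so most delivered support follows the form. This stands. A reader might infer that the change score removes the whole effect of assignment. It removes only the part present when the form is answered, and the documents do not say how large that is. Late return of forms is possible, but no figures bear on it.

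**The timing may be deliberate.** The two items are not shown. If they ask about the assigned program, they have no pre-randomization version, and change from expectation to experience could be the intended construct. That argues against moving the form earlier. It does not make the value a baseline.

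**The 3-month level is not a neutral remedy.** Its near-complete recovery in the simulation is built into the outcome model. If change drives the outcome, as the SAP hypothesizes, and d0 = 0, the level recovers only about 50%. If a stable trait affects both support and outcome (assumed log relative risk 0.2 to 0.4 per unit), the level gives about 126% to 150%. Change cancels such a trait. This also stands, and it is why covariates and a sensitivity analysis belong in the fix.

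**Little rests on it.** Protocol 3.4 lists the mediators under exploratory objectives, and SAP 16.0 runs mediation only for interventions with a significant 6-month effect. Each intervention is compared with usual care, so coach against online is not estimated here. These points limit the scope but do not remove the defect.

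**Conclusion.** The point holds in a limited form. The perceived-support starting value is a post-randomization response to a known arm. It conflicts with the SAP's own definition of a baseline variable, and nothing in SAP 16.0 corrects for it. Following the plan subtracts d0 from d3. That can understate or reverse the arm effect on perceived support, or screen the mediator out.

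The size cannot be fixed from the documents. It ranges from no loss (d0 = 0) through complete loss (d0 = d3) to reversal (d0 > d3). Under the assumptions above, timing lowers the share recovered from about 50% to 25% with half the effect present at notification and to 0% with all of it. In the last case the either-arm screen keeps the mediator at about its null rate of 17.5%. It would be wrong to charge the first 50 points to timing.

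The scope is one of three mediators in exploratory Aim 1c, plus the joint share when perceived support is retained. The primary and secondary effectiveness analyses are unaffected.

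**What to change.** - **SAP 4.0 and 16.0:** define the perceived-support mediator as its 3-month level in Step 2, Step 3a and the weights. Randomization balances the unmeasured pre-assignment value in expectation, so the arm comparison in Step 2 needs no baseline.
- **SAP 16.0, Step 3a:** put pre-randomization covariates into the model. The text already calls for adjustment for baseline confounders, but the printed equation contains only the mediators. Candidates are baseline pain severity, catastrophizing, self-efficacy and mood disorder.
- **Sensitivity analysis:** report the change-from-notification version alongside.
- **Protocol 3.4 and 11.2:** relabel the notification value as an early post-assignment measure and report it by arm, which also shows readers how large d0 was.
- Record the change in the SAP log before the data are unblinded.

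The cost is wording and one variable definition, with no new data. The downsides should be stated in the SAP. A level does not cancel stable personal traits, so it can overstate mediation if the measured confounders are insufficient. Perceived support would also be on a different scale from the other two mediators, which can stay as change scores because their baselines precede randomization.

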11.3 Qualitative Interviews

Patient interviews. A subset of approximately 100 patients will be invited to complete two approximately one-hour long interviews by phone at approximately 3-5 months and 12-14 months post-randomization. A different subset of 20 individuals who do not complete the interventions but are still enrolled in the study (see details related to selection criteria for these interviews in section 6.1) will complete one interview approximately one-hour in length by phone. Interviewers will use semi-structured interview guides for all patient interviews. These interviews will be audio-recorded.

Stakeholder and referring clinician interviews. The stakeholder interviews will be approximately an hour in length and conducted primarily by phone using a semi-structured interview guide; in the instance that a stakeholder is unable to complete the interview in one encounter due to scheduling issues that may arise which allow less an hour for the phone call, follow-up to complete questions may be conducted by phone or email. These interviews will be audio-recorded.

Intervention staff / health coach interviews: Qualitative research team members will attempt to conduct interviews with all (approximately 12) of the intervention/health coaching staff. These interviews will be approximately one-hour in length and conducted twice (early in study implementation and later); they will be audio-recorded.

12 ADVERSE EVENTS AND UNANTICIPATED PROBLEMS INVOLVING RISKS TO SUBJECTS OR OTHERS

12.1 Definition, Classification and Reporting of Adverse Events

12.1.1 *Definition of Adverse Events (AEs)*

An adverse event (AE) is any untoward or unfavorable medical occurrence in a human subject, including abnormal signs, symptoms, or diseases, temporally associated with the subject's participation in the research, whether or not considered related to the subject's participation in the research.

Because the RESOLVE study involves minimal risk and the study population includes patients with high impact chronic pain, who have fluctuating physical and emotional symptoms as part of the natural course of their condition, such symptoms will not be systematically solicited as part of the trial.

AEs will be identified if:

- Participants proactively contacts study staff at any time to self-report an AE;
- Participants happen to self-report an AE during a regular study contact with intervention or study staff; or
- Participants attribute study withdrawal or dropout to unfavorable medical / health-related issues.⁸⁴

AEs will not be solicited uniformly from all study participants, as capture of these events will be biased by study arm (i.e., telephone CBT-CP participants will have greater interaction with study staff by phone and more opportunity to self-report these symptoms and events).

AEs will be entered by study staff into the Utah/DCC REDCap AE database at the time of reporting by the participant.

12.1.2 *Definition of Serious Adverse Events (SAEs)*

For this comparative effectiveness trial, a serious adverse event (SAE) is defined as an event that:

- Results in death during a patient's active participation in the trial.
- Results in inpatient hospitalization during a patient's active participation in the trial. (Planned hospitalization scheduled before the enrollment of a study participant is not an SAE.)

Because the patients who participate in the RESOLVE study will be older and have co-morbid health conditions, it is expected that subjects will experience inpatient hospitalizations, which are unrelated to study participation, during the course of the study. In addition, it is expected that deaths, which are also unrelated to study participation, might occur among study enrollees based on prior studies. Specifically, in the study PI's recently completed pragmatic trial, PPACT, which provided an intensive in-person behavioral intervention and enrolled 850 patients with chronic pain, there were 12 deaths during the study, all unrelated to study participation, and 287 hospitalizations (116 for intervention participants and 171 for usual care).

SAEs will be systematically assessed every 6 months for active study participants based on electronic health records (EHR) data.

- Each clinical site will query active participants' electronic health records data every 6 months (in alignment with the DSMB meeting schedule) to identify any deaths or hospitalizations throughout the interval of active participant enrollment in the trial.
- An independent physician within each health care system/clinical site will conduct a chart review for each death and hospitalization to assess its potential relatedness to study procedures and interventions.
- The summary of SAEs and findings of these reviews will be submitted to the DCC.

In addition to the semi-annual EHR queries, SAEs may be identified by participant self-report. If this occurs, the event will be documented and reviewed by the independent physician as part of the semi-annual review described above.

12.1.3 *Definition of Adverse Events of Special Interest (AESI)*

This protocol will not collect solicited adverse events of special interest (AESI). There is no clinical or empirical basis for hypothesizing that either of the active interventions would increase risk of AESIs. In addition, the unequal contact with study staff among participants in the three study arms inherently results in differential opportunities for ascertainment of "events." Therefore, between-group comparison of adverse events reported to or discovered by study staff would be biased and hence not meaningfully interpretable or actionable.

12.1.4 *Severity of Adverse Events*

For an AE, the following guidelines will be used to describe severity:

- Mild – event does not generally interfere with usual daily activities and/or does not require medical care.
- Moderate – event interferes with usual daily activities and/or requires self-medical care or outpatient medical care.
- Severe – event interrupts usual daily activities and/or requires inpatient medical care or medical care with overnight stay in hospital observation services.

12.1.5 *Relationship to Research Participation*

For an SAE, the following guidelines will be used to describe relatedness to study procedures and study interventions:

- Related – There is clear evidence to suggest a causal relationship between the study procedures or study interventions and the SAE, and other possible contributing factors can be ruled out.
- Possibly Related – There is a reasonable possibility that the study procedures or study interventions caused the SAE. Reasonable possibility means that there is evidence to suggest a causal relationship between the study procedures or study interventions and the SAE.
- Not Related – There is not a reasonable possibility that the study procedures or study interventions caused the SAE, there is no temporal relationship between the study procedures or study interventions and event onset, or an alternate etiology has been established.

12.1.6 *Expectedness of Adverse Events/Serious Adverse Events*

An AE/SAE will be considered unexpected if it occurs in one or more subjects, the nature, severity, or frequency of which is not consistent with either:

- The known or foreseeable risk of adverse events associated with the procedures involved in the research that are described in Section 2; or
- The expected natural progression of any underlying disease, disorder, or condition of the subject(s) experiencing the adverse event and the subject's predisposing risk factor profile for the adverse event.

12.1.7 *Reporting Procedures for Adverse Events/Serious Adverse Events*

Any AEs self-reported by participants to study staff will be entered into the Utah/DCC REDCap AE database.

As described above, every 6 months in alignment with the DSMB meeting schedule, the study sites will provide a summary of SAEs to the DCC.

12.2 *Definition and Reporting of Unanticipated Problems*

12.2.1 *Definition of Unanticipated Problems*

This study protocol uses the following definition of Unanticipated Problems (UPs) to include, in general, any incident, experience, or outcome that meets all of the following criteria:

- Unexpected;
- Related or possibly related to participation in the research; and
- Suggests that the research places participants or others at a greater risk of harm (including physical, psychological, economic, or social harm) than was previously known or recognized.

“Unexpected” means the nature, severity, or frequency is not consistent with either (a) the study procedures or study interventions that are described in section 2; and (b) the characteristics of the participant population being studied.

“Related” means there is clear evidence that the unanticipated problems were caused by the study procedures or study interventions involved in the research and “possibly related” means a reasonable possibility that the unanticipated problem(s) may have been caused by the study procedures or study interventions involved in the research.

12.2.2 *Reporting of Unanticipated Problems*

The study site investigator will report UPs to the lead principal investigator (PI). The lead PI will report UPs to the IRB of record. The UP report will include the following information:

- Protocol identifying information: protocol title and number, PI's name, and the IRB project number
- A detailed description of the event, incident, experience, and/or outcome

- An explanation of the basis for determining that the event, incident, experience, or outcome represents an UP
- A description of any changes to the protocol or other corrective actions that have been taken or are proposed in response to the UP

To satisfy the requirement for prompt reporting, UPs will be reported using the timeline specified in the written reliance agreement between the IRB of record and the relying IRB at each study site.

